#### **1.4 CAMPATH is a novel induction agent with potential benefit**

The Campath-1 (Cambridge Pathology) series of rat monoclonal antibodies was first produced in the early 1980s in the Department of Pathology at the University of Cambridge, UK. The humanised variant of this antibody (Campath-1H - CAMPATH) was expressed in a rat myeloma cell line at Cambridge, and later in Chinese hamster ovary cells at the Wellcome Research Laboratories (13). Clinical investigations of CAMPATH have been conducted in patients receiving solid organ transplantation and in patients with haematological malignancies (14), autoimmune diseases such as rheumatoid arthritis (15), and multiple sclerosis (16).

The Campath-1 antigen (CD52) is an abundant molecule (approximately  $5 \times 10^5$  antibody binding site per cell) that is present on at least 95% of all human peripheral blood lymphocytes and monocytes/macrophages (17). Although antibodies against CD52 are highly effective in depleting lymphocytes by complement and antibody-dependent cell-mediated cytotoxicity (ADCC), this does not appear to be the case for monocytes/macrophages. The antigen has been found on a subpopulation (<5%) of granulocytes but not on human erythrocytes, platelets or bone marrow stem cells. As a consequence, the therapeutic use of antibodies against CD52 does not compromise normal haematopoiesis.

Treatment with CAMPATH rapidly and almost totally depletes the peripheral lymphocyte population. Although B-cells start to re-populate after three months, the T-cell population remains severely depressed for up to 18-24 months (18).

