2.2 Secondary comparisons

The secondary comparisons will be of the incidence of the first occurrence (after maintenance randomisation) of:

- i. Graft outcomes:
 - a. Graft rejection

- i. Biopsy-proven acute rejection: cellular (subdivided into Banff 1, 2, 3 and unknown), humoral (subdivided into Banff 1, 2, 3 and unknown) and all³
 - ii. All rejection: presumed and biopsy-proven (as above)
 - b. Graft survival (with reasons for failure subdivided into glomerular disease, fibrosis/atrophy, medical/surgical condition, rejection or unknown)
 - ii. Safety outcomes:
 - a. Serious infections
 - i. All serious infections: subdivided into opportunistic and non-opportunistic
 - ii. Opportunistic infections subdivided into CMV, BK, fungal (non-invasive and invasive) and other (PCP, mycobacterial and other)
 - iii. Non-opportunistic subdivided into urinary tract, respiratory, gastrointestinal, central nervous system, other/unknown
 - b. Cancer
 - i. All cancer: subdivided into haematological (including post-transplant lymphoproliferative disorder and other); skin (subdivided into non-melanoma and melanoma); lung; gastrointestinal; hepatobiliary; breast; prostate; other/unspecified
 - iii. Other outcomes of interest
 - a. Major vascular events (composite of non-fatal myocardial infarction, cardiac death, non-fatal or fatal stroke and arterial revascularisation)
 - b. Death: subdivided into vascular, infection, cancer and other causes
 - c. Composite of death or graft failure
 - d. Post-transplant diabetes mellitus
 - e. Serious adverse events (subdivided into respiratory, gastrointestinal, hepatobiliary, cardiovascular, musculoskeletal, skin, genitourinary, haematological, other transplant-related, other/unspecified)
 - f. Incidence of anaemia (defined as Hb < 13 g/dL in men, <12 g/dL in women) and severe anaemia (defined as Hb <11 g/dL in men, <10 g/dL in women) [at 3 and 6 months post-randomization only]
 - g. Incidence of leucopenia (defined as total white cell count <3 x 10⁹ cells/mm³) [at 3 and 6 months post-randomization only]
 - h. Incidence of neutropaenia (defined as neutrophil count <2 x 10⁹ cells/mm³) and severe neutropaenia (defined as neutrophil count <1 x 10⁹ cells/mm³) [at 3 and 6 months post-randomization only]
 - i. Incidence of thrombocytopaenia (defined as platelet count <75 x 10⁹ cells/mm³) [at 3 and 6 months post-randomization only]
 - j. Levels of immunosuppressants at 3, 6, 12 and 18 months after randomisation

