3.1 Methods of analysis

The fundamental assessments of efficacy and safety will involve comparisons among all randomized patients in their originally allocated treatment group (i.e. “intention to treat” analyses).^{1, 2} Analyses of categorical outcomes will be based on the first relevant unrefuted event of a particular type (i.e. either confirmed or not refuted during the adjudication process). All time-to-event analyses will be based on the first relevant event, and will use log-rank methods to calculate average event rate ratios (95% confidence intervals) and their associated 2-sided P-values.^{2, 4} Comparisons of continuous outcomes will adjust for the baseline value if available, otherwise two-sample t-tests will be used.

The primary comparison between treatment groups of mean follow-up eGFR at 2 years post-transplantation (ie, on average 18 months post maintenance randomisation) will use analysis of covariance (ANCOVA), adjusted for the baseline value.⁵ The baseline creatinine value used will be the latest value available prior to the maintenance randomisation (including a value from a sample

taken on the day of that randomisation). Any value within 6 months of the anniversary of the date of transplantation will be considered as that year's value. If multiple results are available within this window, the one closest to the anniversary date will be used.

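### SAP 2.2 iii.f–i labels as incidence what is a proportion below a blood-count cut-off at 3 and 6 months, and makes no use of the pre-randomisation count

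*SAP*

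**What the plan says.** SAP 2.2 opens: "The secondary comparisons will be of the incidence of the first occurrence (after maintenance randomisation) of". Items iii.f–i then give four blood-count outcomes by threshold alone: "Incidence of anaemia (defined as Hb < 13 g/dL in men, <12 g/dL in women) and severe anaemia"; "Incidence of leucopenia (defined as total white cell count <3 x 10⁹ cells/mm³) [at 3 and 6 months post-randomization only"; "Incidence of neutropaenia (defined as neutrophil count <2 x 10⁹ cells/mm³", with a severe category below 1; and "Incidence of thrombocytopaenia (defined as platelet count <75 x 10⁹ cells/mm³) [at 3 and 6 months post-randomization only". All four are restricted to 3 and 6 months after randomisation, and none carries a condition on the value at randomisation.

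SAP 3.1 treats the two types of outcome differently. For continuous ones, "Comparisons of continuous outcomes will adjust for the baseline value if available, otherwise two-sample t-tests will be used". For the others, "Analyses of categorical outcomes will be based on the first relevant unrefuted event of a particular type". SAP section 2 stratifies all analyses by induction arm, but not by blood count.

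Protocol 3.5 has no blood-count exclusion at the second randomisation. The minimisation factors it names are graft function, proteinuria and blood pressure. Blood counts are recorded before that point: at discharge (Protocol 3.3.5) and at certain follow-up visits (3.4.3). The schedule in Appendix 6 appears to include month 6, although its columns are broken in the text available.

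**The concern.** Incidence of a first occurrence implies that participants start free of the condition. Nothing in iii.f–i ensures this. A man with Hb 12 g/dL at randomisation and 12 g/dL three months later meets the definition although nothing has changed. The plan does not say whether he is a first occurrence, is excluded, or is adjusted for. Taken as written, he counts.

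Some participants will plausibly be low at entry. All take mycophenolate, and Protocol 4.2.4.3 has a dose table for neutropaenia. The anaemia cut-off is mild. After CAMPATH, "the T-cell population remains severely depressed for up to 18-24 months", which bears on the white cell count through lymphocytes.

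At stake is how the results on cytopenia after conversion to sirolimus are read. A reader told *incidence* will take the figures as cytopenia arising after conversion, and will take the ratio as the effect on new onset. Both readings would be wrong if many were already low. Separately, a count that predicts later counts is left unused, which wastes precision.

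**Working it through.** The documents give no rate, power or baseline prevalence for these outcomes, so there is no figure to reproduce.

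**Inputs.** Two-sided alpha of 0.05 (the conventional level named in SAP 3.3). Everything else is assumed: n = 200 per arm (the protocol has 800 at the first randomisation but does not say how many reach the second); new anaemia r = 15% on tacrolimus and 30% on sirolimus (ratio 2.0); a share b already below the cut-off; persistence q among them.

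**Formulas.** Proportion below the cut-off in an arm: p = b·q + (1 − b)·r. Power = Φ{[|p1 − p2| − 1.96·√(2p̄(1 − p̄)/n)] / √[(p1(1 − p1) + p2(1 − p2))/n]}. For new onset only, p is 0.15 or 0.30 and n is 200(1 − b).

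**Step 1: no drug effect in those already low (q = 0.80 in both arms).** At b = 0.20, tacrolimus: 0.20×0.80 + 0.80×0.15 = 0.28; sirolimus: 0.16 + 0.80×0.30 = 0.40. The ratio is 0.40/0.28 = 1.43. At b = 0.01 the proportions are 0.1565 and 0.305, ratio 1.95. At b = 0.05 they are 0.1825 and 0.325, ratio 1.78 and power 91%.

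**Step 2: same odds ratio in those already low.** The odds ratio is (0.30/0.70)/(0.15/0.85) = 2.43. Persistence of 60% on tacrolimus (odds 1.5) becomes 3.64/4.64 = 78.5% on sirolimus. Persistence of 80% (odds 4) becomes 9.71/10.71 = 90.7%.

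| Already low (b) | All patients, step 1: ratio; power | Step 2, 60% persistence: ratio; power | Step 2, 80% persistence: ratio; power | New onset only: ratio; power |
|---|---|---|---|---|
| 20% | 1.43; 72% | 1.65; 92% | 1.50; 84% | 2.0; 90% |
| 35% | 1.26; 50% | 1.53; 92% | 1.36; 78% | 2.0; 83% |
| 50% | 1.16; 32% | 1.45; 92% | 1.27; 73% | 2.0; 72% |

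The ratio moves towards 1 in every row. Power falls well below the new-onset analysis only in step 1. In step 2 it ranges from somewhat below to well above.

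**Step 3: value of the baseline count for the binary outcome.** In a simulation of a continuous blood value (200 per arm, 600 runs per setting, drug shift of −0.35 SD, baseline correlation 0.5 or 0.7, 20–60% already low), power was 75–82% for all patients unadjusted, 49–70% for new onset only, and 83–92% for all patients adjusted for baseline. With no drug effect, rejection stayed near 5% for all three.

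**Step 4: continuous comparison by the SAP 3.1 method.** Assume a 0.3 SD shift, correlation 0.6 and 200 per arm. The adjusted standard error is √(1 − 0.36)·√(2/200) = 0.08 SD, so power is about Φ(0.3/0.08 − 1.96) = Φ(1.79) = 96%. For the unadjusted cut-off with 20% below it on control, the sirolimus proportion is Φ(−0.842 + 0.3) = 0.294, and 0.294 against 0.20 has power of about 59%. With 5% below, 0.089 against 0.05 has about 34%. With 50% below, 0.618 against 0.50 has about 66%.

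**The case against.** The strongest reply is that the comparison is valid as it stands. Randomisation balances baseline counts in expectation, and the proportion below a threshold among all those allocated is a legitimate intention-to-treat measure. It also captures a drug that keeps low patients low, which a new-onset analysis misses. This stands. It is why the fix keeps everyone in and changes the label and the adjustment, not the population.

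A reader might infer that counting already-low patients necessarily dilutes the drug effect and costs power, so that a real safety signal would be hidden. The documents do not support this. It needs a high baseline prevalence, which they do not give, and no drug effect in those already low, which nothing in them states. Step 2 shows power holding when the second condition is dropped.

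A reader might also extend the point equally to all four outcomes on the strength of the 18–24 month depletion. That figure concerns T cells. The same section of the protocol says that the target antigen is absent from red cells, platelets and marrow stem cells. Appendix 8 places thrombocytopenia mainly in weeks 2–4 and neutropenia in weeks 4–8, well before month 6. Few patients may be below platelets <75 or neutrophils <1 at entry, and the ratio then barely moves.

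Finally, these outcomes are not the only evidence on cytopenia. Haematological serious adverse events (iii.e) and reasons for stopping treatment (iv.a) also contribute.

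**Conclusion.** The point holds as one of labelling and precision. As written, iii.f–i measure the proportion below a cut-off at two visits, not new cytopenia, and leave the pre-randomisation count unused.

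The risk ratio can be pulled towards 1 where many are low at entry. That is plausible for mild anaemia, possible for leucopenia and mild neutropaenia, and less likely for platelets <75 or severe neutropaenia. Under the stated assumptions, a new-onset ratio of 2.0 reads as 1.16–1.65 with 20–50% already low, and as 1.95 with 1%. The size in this trial is unknown without the baseline prevalence.

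The precision lost by ignoring baseline depends less on that prevalence. With the assumed shift and correlation, the baseline-adjusted continuous comparison has about 96% power, against about 34–66% for the unadjusted cut-off.

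There is no bias under the null. These are secondary outcomes, and the primary eGFR result is untouched. The change is a free improvement, not the repair of an invalid analysis.

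**What to change.** In SAP 2.2 iii.f–i:

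- Replace *incidence* with *proportion below the cut-off at 3 and 6 months post-randomisation*, and exempt these items from the first-occurrence lead-in.
- Keep all randomised participants. Adjust for the latest value before maintenance randomisation (for example by logistic regression), stratified by induction arm as already planned.
- Add Hb, white cells, neutrophils and platelets at 3 and 6 months as continuous outcomes, compared by the baseline-adjusted method already in SAP 3.1.
- Report new onset among those above the cut-off at baseline as a supporting analysis only. It drops randomised participants and can lose power.
- Show by arm the number below each cut-off at baseline, so that readers can judge how far the ratios reflect existing cases.

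The cost is SAP wording and a few extra models, with no new data collection planned. Two details need settling: confirm from the intact schedule that a month-6 blood count is collected, and state how a missing pre-randomisation count is handled.

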#### 3.4.3 *Blood results*

At each follow-up visit, results for creatinine and therapeutic drug level monitoring will be recorded, as well as a full blood count, lipid profile (total cholesterol, HDL-cholesterol and triglycerides if available) and urinary protein:creatinine ratio at certain visits. These will be copies of results of routine clinical tests requested by the managing team. See Appendix 6: Schedule of study procedures.

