#### 4.6 Appendix 6: Schedule of study procedures

		Visit						Questionnaire				
		Transplant surgery	Discharge	Month								
				1	3	6	9	12	24	36	48	60
Check eligibility	•											
Medical history	•	•										
Informed consent	•											
First randomisation	•											
Second randomisation					•							
Quality of life assessment		•	•	•	•	•	•	•	•	•	•	•
Laboratory results	Renal function*	•	•	•	•	•	•	•	•	•	•	•
	Lipid profile†	•			•		•					
	FBC‡	•		•	•	•	•					
	Immunosuppressant level	•	•	•	•	•	•	•	•	•	•	•
	Urine protein:creatinine ratio		•	•	•	•	•	•				

\* serum creatinine

† total cholesterol, HDL-cholesterol and triglycerides

‡ including white cell differential

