 - k. Proteinuria (compared by calculating ratio of geometric means) [at 3 and 6 months post-randomization only]. If albumin:creatinine ratio (ACR) value is available but not protein:creatinine ratio (PCR) for a given time-point, then it will be converted to PCR by the formula PCR = ACR x 1.6
 - l. Total cholesterol, HDL-cholesterol, non-HDL-cholesterol and triglyceride concentrations, and use of lipid-lowering therapy [at 6 months post-randomization only]
 - iv. Tolerability

- a. Reasons for stopping allocated treatment subdivided into suspected serious adverse reactions, serious adverse events (subdivided as in iii.e above), non-serious adverse reactions (including proteinuria, deteriorating graft function and other NSARs in same categories as SAEs) and other reasons (patient wishes or other)

These analyses will be conducted when all participants have completed 2 years and at a median follow-up of 5 years after transplantation. Participants will be censored at the date at their date of death or the date on which they were last known to be alive (based on flagging with the Office for National Statistics) once 2 (or 5) years have elapsed after the last patient was transplanted.

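### SAP 2.2 pre-specifies the four blood counts only as incidence below a cut-off; adding comparisons of the recorded values would detect a general shift with more power

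*SAP*

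**What the plan says.** SAP 2.2, in the group headed as other outcomes of interest, lists four blood-count items, all at 3 and 6 months after randomisation only:

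- iii.f: "Incidence of anaemia (defined as Hb < 13 g/dL in men, <12 g/dL in women) and severe anaemia", with a lower pair of limits for the severe grade.
- iii.g: "Incidence of leucopenia (defined as total white cell count <3 x" 10⁹.
- iii.h: "Incidence of neutropaenia (defined as neutrophil count <2 x" 10⁹, with a severe grade below 1.
- iii.i: "Incidence of thrombocytopaenia (defined as platelet count <75 x" 10⁹.

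These limits are the event definitions in protocol Appendix 1. The numerical results are collected: protocol 3.4.3 records creatinine and drug levels "as well as a full blood count, lipid profile" and urine protein at certain visits, and Appendix 6 specifies the blood count as "including white cell differential".

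Two other laboratory items in the same SAP list stay on their measured scale. Item iii.k is "Proteinuria (compared by calculating ratio of geometric means", and iii.l lists lipid concentrations. SAP 3.1 supplies a general rule: "Comparisons of continuous outcomes will adjust for the baseline value if available, otherwise two-sample t-tests will be used". SAP 2 stratifies all analyses by induction arm. SAP 2.3 adds exploratory analyses that include laboratory results, without naming a count, scale, timepoint or method.

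**The concern.** Reducing a measured count to above or below a line discards how far each patient moved. If conversion to sirolimus lowers a count modestly in most patients, few of them cross the line, most of all where the limit is one that few controls fall below. The test then has little chance of showing a difference that the recorded values could show.

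The plan already holds the data and a suitable method, and uses the measured scale for proteinuria and lipids. It gives no reason for treating the blood counts differently. At stake is the sensitivity of a few secondary comparisons of possible harm: a null result on a sparse cut-off is weak evidence that the counts are unaffected.

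**Working it through.** **Plan's own figure.** The documents state no power or sample size for the blood counts, so there is nothing to reproduce on this point.

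**Inputs from the documents.** Two-sided 0.05 is the conventional level described in SAP 3.3, with no formal adjustment of secondary comparisons. Protocol 2.1 gives 800 patients at the first randomisation; the number entering the second is not stated.

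**Assumed inputs.** 200 or 300 analysed per arm (50% or 75% of 800); normally distributed values (after logs where needed); a uniform shift d of 0.20, 0.25 or 0.30 SD; a share p₁ of controls below the cut from 1% to 50%. A two-proportion test stands in for the incidence comparison.

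**Formulas**

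- Values: power = Φ( d / [√(1−r²)·√(2/n)] − 1.96 ), where r is the correlation with baseline (r = 0 if unadjusted).
- Cut-off: p₂ = Φ(Φ⁻¹(p₁) + d); power = Φ( [(p₂ − p₁) − 1.96·SE₀] / SE₁ ), where SE₀ uses the pooled and SE₁ the separate variances.

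**Worked case, n = 300, d = 0.25**

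- Values: 0.25/√(2/300) = 0.25/0.0816 = 3.06; Φ(3.06 − 1.96) = 86%. With r = 0.5 this rises to 94%.
- Cut-off, p₁ = 5%: p₂ = Φ(−1.645 + 0.25) = 8.15%; SE₀ and SE₁ are both about 0.0202; Φ([0.0315 − 0.0397]/0.0202) = 34%.

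| d = 0.25 SD | Values, unadjusted | Cut-off: 40% of controls below | 20% | 5% | 1% |
|---|---|---|---|---|---|
| 300 per arm | 86% | 68% | 60% | 34% | 15% |
| 200 per arm | 71% | 51% | 44% | 25% | 11% |

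**Other shifts.** Over the whole grid the smallest unadjusted gap is at 300 per arm, d = 0.30 and 40% below: 95.7% against 83.2%, about 12 points. At 200 per arm, d = 0.20 and 40% below, it is 51.6% against 35.4%, about 16 points.

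**Why rarity matters.** For a small uniform shift, the efficiency of one cut-off relative to the means is φ(Φ⁻¹(p₁))²/[p₁(1−p₁)]. That is 0.64 at 50% below (the best case), 0.62 at 40%, 0.22 at 5% and 0.07 at 1%.

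**The opposite pattern.** Suppose a fraction f of sirolimus patients fall by D SD and the rest do not move, with 2% of controls below the cut and 300 per arm.

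- f = 5%, D = 3. Below the cut on sirolimus: 0.95×0.02 + 0.05×Φ(−2.054 + 3) = 6.0%, giving cut-off power of 71%. Mean shift: 0.05×3 = 0.15 SD; variance in that arm: 1 + 0.05×0.95×9 = 1.43; SE = √((1 + 1.43)/300) = 0.090; power on the values = Φ(1.67 − 1.96) = 38%.
- f = 10%, D = 2. Cut-off power is 79% and power on the values 62%.

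Which scale has more power therefore depends on the shape of the effect.

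**The case against.** The case for leaving the SAP alone is substantial. The cut-offs are the protocol's own defined events, and the neutrophil limits of 2.0 and 1.0 match the bands in its MPA dose table (4.2.4.3). How many patients cross such a line is a legitimate clinical question, different from whether the mean moved. The items are listed among other outcomes of interest, apart from the SAP's safety group of infections and cancer. Haemoglobin and neutrophils each have two limits. Haematological serious adverse events are compared (iii.e), and haematological reasons for stopping treatment are tabulated (iv.a). SAP 3.3 ties reliability to the number of events, so the plan does not invite reassurance from a sparse null result.

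Most of this stands, and it rules out two inferences a reader might draw. The first is that the incidence tests should give way to tests of means. The few-patients calculation shows that this could lose power for steep falls, and it would remove the test of events the protocol names. The second is that the values will not be analysed at all. SAP 2.3 does allow exploratory laboratory analyses.

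What does not stand is that the exploratory line closes the gap. With no count, timepoint or method named, and with its results to be discounted as retrospective, it is not a pre-specified comparison. Nor does a second, more severe limit recover the lost information, since fewer patients fall below it.

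**Conclusion.** The point holds as a limited loss of sensitivity. It is not an error or a contradiction. For a general shift, the pre-specified cut-off tests lose at least about 12 percentage points of power over the range examined, and far more where few controls fall below the limit (86% against 15% at 1% below, for 0.25 SD and 300 per arm). All of this rests on assumed sample sizes, shifts, normality and control prevalences, because the documents give none of them for the blood counts.

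A reader might infer that a real marrow effect of sirolimus would usually be missed. The documents do not support that: they state no expected effect on the counts and no prevalence below any limit, and a steep fall in a few patients favours the cut-off. The point is minor, concerns other outcomes of interest, and leaves the primary eGFR comparison untouched.

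**What to change.** Keep the incidence comparisons in SAP 2.2 iii.f-i as they are. Beside them, pre-specify between-arm comparisons of recorded haemoglobin, white cells, neutrophils and platelets at 3 and 6 months after randomisation, under the existing SAP 3.1 rule: adjusted for the value at maintenance randomisation where available, stratified by induction arm, and on the log scale for white cells, neutrophils and platelets. State how missing counts are handled, since SAP 3.2 covers eGFR, drug levels, urine protein and lipids but not blood counts.

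The cost is a few sentences and a few model fits on data already collected. The downside is a few more secondary comparisons to interpret under SAP 3.3.
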